4.3 Secondary Endpoints

- On treatment safety, as measured by frequency of deaths, SAEs, discontinuations due to AEs, Grade 3/4 AEs, and Grade 3/4 laboratory abnormalities through the end of treatment plus 7 days;
- The proportion of subjects who achieve HCV RNA < LLOQ, TD or TND at each of the following Weeks: 1, 2, 4, 8, 12, 16, 20, 24, and EOT; post-treatment Weeks 4 and 24;
- The proportion of subjects who achieve HCV RNA < LLOQ, TND at each of the following Weeks: 1, 2, 4, 8, 12, 16, 20, 24, and EOT.

4.4 Exploratory Endpoints

5 SAMPLE SIZE AND POWER

Table 5.1-1 presents some scenarios of observed SVR12 rates and exact binomial 95% confidence intervals.

Table 5.1-1: SVR12 Observed Rates and Exact Binomial 95% Confidence Intervals (n = 75)

Observed SVR12 Rate	Observed Responders	95% CI
71%	53 of 75	(59.0%, 80.6%)
76%	57 of 75	(64.7%, 85.1%)
80%	60 of 75	(69.2%, 88.4%)
85%	64 of 75	(75.3%, 92.4%)
91%	68 of 75	(81.7%, 96.2%)
96%	72 of 75	(88.8%, 99.2%)

6 STUDY PERIODS, TREATMENT REGIMENS AND POPULATIONS FOR ANALYSES

6.1 Study Periods

Refer to core Statistical Analysis Plan (Core SAP) Section 6.1.

6.2 Treatment Regimens

All subjects are given the same treatment regimen, DCV+ SOF with RBV through Week 24.

6.3 Populations for Analyses

This is a non-randomized study. Populations for analyses include the following: Enrolled Subjects, Treated Subjects, and Follow-up Subjects. Refer to core SAP Section 6.3 for description of Population for Analyses.

7 STATISTICAL ANALYSES

Statistical analyses are performed using the version of UNIX SAS or S-Plus in production, unless otherwise specified.

7.1 General Methods

Laboratory abnormalities are determined from laboratory measurements analyzed at the central or local laboratory.

Otherwise, refer to Core SAP Section 7.1.

There is only one treatment regimen in this study. Analyses are planned to be presented for all treated subjects by prior HCV therapy status (naive, experienced), coinfection status (HCV monoinfected, HCV/HIV coinfecte) and overall. Depending on enrollment, if only a minimum number of HCV/HIV coinfecte subjects are enrolled, Analyses will be presented by prior HCV therapy status (naive, experienced) and overall.

7.2 Study Conduct

Refer to Core SAP Section 7.2.

[Appendix 1](#) describes the relevant protocol deviations of this study that can be programmed from the database.

7.3 Study Population

7.3.1 Disposition of Subjects

Refer to Core SAP Section 7.3.

[figure not shown]
7.3.2 Demographics and Other Baseline Characteristics

7.3.2.1 Demographics

Refer to Core SAP Section 7.3.2.1.

7.3.2.2 Baseline Disease Characteristics and Prognostic Factors

All subjects in this study are GT-3 Infected with cirrhosis.

Otherwise, refer to Core SAP Section 7.3.2.2.

7.3.2.3 *Other Baseline Characteristics*

Refer to Core SAP Section 7.3.2.3.

7.4 *Extent of Exposure*

Study therapy of this study is DCV+SOF+RBV.

Refer to Core SAP Section 7.4. In addition, proportions of subjects with RBV dose reduction, and RBV discontinuation will be presented separately. RBV discontinuation will be defined as last RBV dosing date < last treatment dosing date -1. Time to the first RBV dose reduction and time to RBV discontinuation will also be summarized.

Subjects with full RBV dosing, dose reduction or interruptions > 14 days are summarized. A subject listing is generated for all subjects who received a full RBV dose or experienced a reduction or interruption in RBV dose. This listing will include time on study therapy, treatment start and stop dates, weight, target daily dose, total daily dose received, reason for modification, duration adherence, and dose adherence.

7.5 *Efficacy*

For binary efficacy endpoints, 2-sided 95% CIs will be calculated based on exact binomial distribution.

7.5.1 *Primary Efficacy Endpoint*

The primary analysis will be performed after all subjects have reached post-treatment Week 12 (SVR12). A final analysis (SVR24) will be performed at study completion.

The primary analysis for the primary endpoint SVR12 will be computed on all treated subjects, and missing HCV RNA data at follow-up Week 12 will be imputed using the Next Value Carried Backwards (NVCB) approach, ie, missing HCV RNA data in the follow-up Week 12 window

will be imputed using the next and closest available HCV RNA measurement after the follow-up Week 12 HCV RNA visit window.

The lower bound of the SVR12 95% confidence interval (CI) will be used to compare to the historical threshold of 79%. If it exceeds 79%, it can be concluded that the primary objective is achieved.

The following sensitivity analyses on the primary endpoint will also be conducted:

- Sensitivity analysis using mITT (Missing=Non-Responder): SVR12 rates and two-sided 95% CIs will use all treated subjects. The SVR12 status for subjects with missing follow-up Week 12 HCV RNA will be counted as non-responders.
- Sensitivity analysis using observed values: SVR12 rates and two-sided 95% CIs will be computed on subjects with observed HCV RNA values. The numerator is based on subject meeting the response criteria. However, the denominator is based on treated subjects with observed HCV RNA at post-treatment Week 12.

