3.5 Discontinuation of Subjects following any Treatment with Study Drug

Subjects MUST discontinue investigational product (and non-investigational product at the discretion of the investigator) for any of the following reasons:

- Subject's request to stop study treatment
- Any clinical adverse event (AE), laboratory abnormality or intercurrent illness which, in the opinion of the investigator, indicates that continued participation in the study is not in the best interest of the subject
- Termination of the study by Bristol-Myers Squibb (BMS)

- Loss of ability to freely provide consent through imprisonment or involuntarily incarceration for treatment of either a psychiatric or physical (eg, infectious disease) illness
- Pregnancy
- Laboratory or Clinical Criteria: If any of the following laboratory or clinical criteria is obtained for any patient, the result must be repeated /confirmed within 72 hours and the BMS central medical monitor should be informed. If the results are confirmed, the patient must discontinue treatment. Clinical criteria must have Principal Investigator or Sub-Investigator assessment prior to proceeding to permanent discontinuation
 - Evidence of confirmed hepatic decompensation (Child-Pugh Class B or C, Score > 6)
 - ALT > 2 × baseline and 5 × ULN, and either total bilirubin > 2 × ULN or INR > 2
 - Any Grade 4 AE or clinically significant laboratory abnormality considered study drug-related (see [Section 6.3](#) for laboratory abnormality AE reporting requirements).
- Virologic Breakthrough (confirmatory results must be obtained 2 weeks from the original result) defined as:
 - Confirmed $\geq 1 \log_{10}$ IU/mL HCV RNA on-treatment increase from nadir, or
 - Confirmed increase in HCV RNA \geq LLOQ if HCV RNA previously declined to < LLOQ TD/TND.

If discontinuation of therapy is required, this must occur no later than the next study visit.

Any subject who receives anti-HCV therapy in the post-treatment period prior to Post-Treatment Week 4 (ie, a subject who discontinued therapy due to an AE or virologic failure), who then chooses to receive an alternative therapy (outside of the study), should discontinue from the study after completing the Post-Treatment Week 4 safety visit (see [Table 5.1-3](#)). If the subject receives HCV therapy after Post-Treatment Week 4, the subject should be discontinued from the study as soon as possible, following completion of the procedures outlined in the Post-Treatment Week 24 visit.

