8.4.2.1 Primary Efficacy

The primary analysis will be performed after all subjects have completed post-treatment Week 12 (SVR12). A final analysis (SVR24) will be performed at study completion.

The primary analysis for the primary endpoint SVR12 will use all treated subjects, and missing HCV RNA data at follow-up Week 12 will be imputed using the Next Value Carried Backwards (NVCB) approach, ie, missing HCV RNA data in the follow-up Week 12 window will be imputed using the next and closest available HCV RNA measurement after the follow-up Week 12 HCV RNA visit window.

The lower bound of the SVR12 95% confidence interval (CI) will be used to compare to the historical threshold of 79%. If it exceeds 79%, it can be concluded that the primary objective is achieved.

The following sensitivity analyses on the primary endpoint will also be conducted:

- Sensitivity analysis using mITT: SVR12 rates and two-sided 95% CIs will use all treated subjects. The SVR12 status for subjects with missing follow-up Week 12 HCV RNA will be counted as non-responders
- Sensitivity analysis using observed values: SVR12 rates and two-sided 95% CIs will use observed values. The numerator is based on subject meeting the response criteria. However, the denominator is based on treated subjects with HCV RNA at post-treatment Week 12

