2 STUDY DESCRIPTION

2.1 Study Design

Study design schematic is presented in Figure 2.1-1.

Figure 2.1-1: Study Design Schematic

Subjects with GT-3 Infection with Cirrhosis

AI444379 is an open label, one-arm trial evaluating the combination therapy of DCV and SOF plus RBV for 24 weeks duration in GT-3 subjects with cirrhosis.

Subjects will receive the combination of DCV 60 mg QD (unless concomitant HIV regimen dictates otherwise) + SOF 400 mg QD + RBV (weight based 1000 mg-1200 mg daily) for 24 weeks.

As an open label study, HCV RNA will be available for review by the clinical site personnel. Any subject who discontinues therapy before the protocol-defined treatment duration should have 24 weeks of post-treatment follow-up. The screening/enrollment period is anticipated to be approximately 8 weeks from FPFV to LPFV. Study duration will be 52 weeks (4 week screening period, 24 weeks of therapy, and 24 weeks of follow-up).

Any subject who receives anti-HCV therapy in the post-treatment period prior to Week 4 (i.e., a subject who discontinued therapy due to an AE or virologic failure who then chooses to receive an alternative therapy outside of the study), should discontinue from the study after completing the post-treatment Week 4 safety visit. If the subject receives HCV therapy after post treatment Week 4, the subject should be discontinued from the study as soon as possible, following completion of the procedures outlined in the Post-treatment Week 24 visit.

The end of the study is defined as the date of the last visit for the last subject to complete the study. The last visit is defined as the last post-treatment follow up subject visit.

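### The observed-values SVR12 sensitivity analysis can drop confirmed virologic failures that have no Week 12 value; count those subjects as non-responders

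*SAP*

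**What the plan says.** Protocol 8.4.2.1 and SAP 7.5.1 set out three analyses of SVR12.

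- **Primary.** All treated subjects. A missing Week 12 value is "imputed using the next and closest available HCV RNA measurement after the follow-up Week 12 HCV RNA visit window" (next value carried backwards, NVCB). The 79% comparison is attached to this analysis.
- **mITT sensitivity.** All treated subjects. "The SVR12 status for subjects with missing follow-up Week 12 HCV RNA will be counted as non-responders".
- **Observed-values sensitivity.** In the protocol, "the denominator is based on treated subjects with HCV RNA at post-treatment Week 12". The SAP has the same rule and adds the word observed: "the denominator is based on treated subjects with observed HCV RNA at post-treatment Week 12".

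SAP Table 8.1-1 sets the follow-up windows: Week 4 is > 1 to 8 weeks, Week 12 is > 8 to 18 weeks, and Week 24 is > 18 weeks.

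Three other provisions bear on who has a Week 12 value.

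- **Breakthrough.** Under protocol 3.1 and 3.5 it must be confirmed ("confirmatory results must be obtained 2 weeks from the original result") and leads to stopping therapy.
- **Exit rule.** SAP 2.1 gives as its example "a subject who discontinued therapy due to an AE or virologic failure who then chooses to receive an alternative therapy" outside the study. If that therapy starts before post-treatment Week 4, the subject "should discontinue from the study after completing the Post-Treatment Week 4 safety visit" (protocol 3.5). If it starts later, the subject leaves as soon as possible, "following completion of the procedures outlined in the Post-Treatment Week 24 visit".
- **Default.** Subjects who stop early are otherwise followed for 24 weeks after treatment (protocol 3.1 and 3.6).

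**The concern.** A sensitivity analysis for missing data should vary what is assumed about outcomes that nobody knows. A subject with confirmed breakthrough or confirmed relapse who then leaves for other therapy lacks a Week 12 measurement, but the outcome is known. Under the observed-values rule that subject is handled like someone lost to follow-up with undetectable virus.

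The exclusion then depends on the outcome. The subject is missing at Week 12 because treatment failed, and removing such subjects moves the rate in one direction only. At stake is one supporting figure, which could look better than the primary result because documented failures were set aside.

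**Working it through.** **Inputs.** N = 75 treated (planned size, protocol 3.1). R = 68 responders (a row of SAP Table 5.1-1, used here as an assumed result). Two-sided 95% exact binomial intervals (SAP 7.5). k = number of confirmed failures with no Week 12 value. The documents do not give k, so it is assumed to lie between 0 and 3.

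**Step 1: reproduce the plan's figure.** For x responders of n, the exact lower bound is the 0.025 quantile of Beta(x, n − x + 1) and the upper bound is the 0.975 quantile of Beta(x + 1, n − x). For 68/75 this gives 90.7% (81.71%, 96.16%), which agrees with the 81.7% and 96.2% in Table 5.1-1.

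**Step 2: can the plan produce such a subject?**

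- Failure is confirmed on treatment, therapy stops, and outside therapy starts before post-treatment Week 4. The subject leaves after the Week 4 visit. That visit falls in the > 1 to 8 week window, so there is no Week 12 value.
- Outside therapy starts after Week 4. The exit visit follows the Week 24 procedures, and HCV RNA is among the Week 24 assessments (protocol 5.4.2). An exit after Week 8 and by Week 18 supplies a value in the Week 12 window, so the subject stays in. An exit by Week 8 does not.
- A confirmed failure may also withdraw consent or be lost (protocol 3.6.1, 3.6.2).

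So the route exists, but it is narrow.

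**Step 3: size when nothing else is missing.** The rate as written is R/(N − k). With confirmed failures kept it is R/N. The ratio is N/(N − k).

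| k | As written | Lower 95% bound | Failures kept | Lower 95% bound | Ratio |
|---|---|---|---|---|---|
| 0 | 68/75 = 90.7% | 81.7% | 68/75 = 90.7% | 81.7% | 1 |
| 1 | 68/74 = 91.9% | 83.2% | 68/75 = 90.7% | 81.7% | 75/74 = 1.014 |
| 2 | 68/73 = 93.2% | 84.7% | 68/75 = 90.7% | 81.7% | 75/73 = 1.027 |
| 3 | 68/72 = 94.4% | 86.4% | 68/75 = 90.7% | 81.7% | 75/72 = 1.042 |

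**Step 4: a mixed case.** Assume 64 responders at Week 12, 4 responders with only a later value, 6 failures with a Week 12 value and 1 confirmed failure without one (64 + 4 + 6 + 1 = 75).

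| Analysis | Rate | Lower 95% bound |
|---|---|---|
| Observed values, as written | 64/(64 + 6) = 64/70 = 91.4% | 82.3% |
| Observed values, confirmed failure kept | 64/(64 + 6 + 1) = 64/71 = 90.1% | 80.7% |
| Primary (NVCB) | (64 + 4)/75 = 68/75 = 90.7% | 81.7% |
| mITT | 64/75 = 85.3% | 75.3% |

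Keeping the confirmed failure lowers the observed-values figure by 1.3 points. The result repeats neither the primary nor the mITT figure. The 4 later responders stay excluded and pull the figure down, so its distance from the primary is not given by N/(N − k).

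**The case against.** The strongest reply is that an observed-case analysis uses observed values by definition. The plan labels it that way, and the primary and mITT analyses beside it keep every treated subject in the denominator, so a reader can compare all three. This largely stands: the rule is a choice of analysis and not an arithmetic error, and its consequences are contained. It does not answer why a confirmed failure should be handled as an unknown when the data to classify that subject are already in hand.

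Three further objections stand in full.

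- **k may be 0.** The default is 24 weeks of follow-up and the Week 12 window is wide.
- **The net direction is not fixed.** Later responders are dropped too, which works the other way.
- **Some handling may be specified elsewhere.** SAP 8.2 (Domain Derivations) shows no text in the public copy, and the Core SAP is not among the documents. The absence of an exception is therefore claimed only for the visible text, although the denominator in SAP 7.5.1 is stated outright and does not defer to the Core SAP.

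Two stronger remedies are tempting and should not be adopted. One is to exclude only subjects with a wholly unknown outcome, using later values where they exist. That would bring NVCB into the one analysis that has no imputation, and the primary already uses NVCB. The other is to treat any last HCV RNA at or above LLOQ as failure. Entry requires at least 10,000 IU/mL (protocol 3.3.1), so a subject lost soon after Day 1 would become a known failure without the confirmation that protocol 3.1 requires.

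**Conclusion.** The point holds as a low-priority improvement. As written, the observed-values analysis can remove subjects because they failed, and each such removal can only raise the figure. Under the assumed 68 of 75 with nothing else missing, the rise is 1.2, 2.5 or 3.8 percentage points for k = 1, 2 or 3, and nothing for k = 0.

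A reader might infer more than this, and the documents do not support it.

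- **That the rule could turn a failed trial into a success.** With 66 responders and 9 failures, 4 of them without a Week 12 value, the all-treated lower bound is 78.4% (66/75) and the observed-values lower bound is 84.3% (66/71). But the 79% criterion applies only to the primary analysis, and nothing in the documents suggests that 4 of 9 failures would lack a value.
- **That known failures will in fact be dropped.** The documents show only that they can be.
- **That the figure is always too high by N/(N − k).** That holds only when no later responders are dropped.

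**What to change.** In the observed-values bullet of protocol 8.4.2.1 and SAP 7.5.1, define the denominator as the sum of two groups:

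1. treated subjects with an observed HCV RNA in the Week 12 window, classified by that value;
2. treated subjects without one who had confirmed on-treatment virologic breakthrough, or confirmed post-treatment HCV RNA at or above LLOQ after a value below LLOQ (TD or TND) at EOT, counted as non-responders.

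Leave all other subjects without a Week 12 value excluded, and report the number in each of the three groups so that k is visible. Group 2 needs its own wording because the relapse definition in protocol 3.1 requires TND at EOT and would miss a subject who was TD. Do not add NVCB to this analysis, and do not count an unconfirmed last value at or above LLOQ as failure. Relabel the analysis as observed values, with confirmed virologic failures counted as non-responders.

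The cost is one short edit in each document and minor programming on HCV RNA already collected. The sensitivity estimate may come out slightly less favourable.

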7.5.2 Secondary and Other Efficacy Endpoints

7.5.2.1 HCV RNA < LLOQ TD or TND Over Time

The proportion of subjects who achieve HCV RNA < LLOQ TD or TND are presented at each of the following Weeks: 1, 2, 4, 8, 12, 16, 20, 24, and EOT; post-treatment Weeks 4, 12 and 24. Otherwise, refer to Core SAP Section 7.5.2.1.

7.5.2.2 HCV RNA < LLOQ TND Over Time

The proportion of subjects who achieve HCV RNA < LLOQ TND at each of the following Weeks are presented: 1, 2, 4, 8, 12, 16, 20, 24, and EOT; post-treatment Weeks 4, 12 and 24. Otherwise, refer to Core SAP Section 7.5.2.2.

[figure not shown]
7.5.2.3 HCV RNA Changes from Baseline

[figure not shown]
Refer to Core SAP Section 7.5.2.3.

7.5.2.4 Concordance between SVR12 and SVR24

Refer to Core SAP Section 7.5.2.4.

7.5.2.5 Efficacy Results in Subgroups

7.6 Safety

Safety endpoints are assessed for all treated subjects, unless otherwise specified. Refer to Core SAP Section 7.6, which includes Sections 7.6.1 to 7.6.11

7.7 Pharmacokinetic Analyses

The Pharmacokinetic (PK) samples collected from the current study may be pooled to perform an integrated population PK analysis, the results of which may be reported separately. All available individual plasma concentrations from all subjects will be listed by nominal time.

7.7.1 Trough Concentrations

Pre-dose PK trough samples are collected at weeks 1, 2, 4, 8, 12 and 24 from all treated subjects.

Analyses are based on evaluable PK trough concentrations. The trough concentrations of DCV and possibly SOF and its metabolites (pending the assay availability) from evaluable PK trough samples will be summarized based on nominal time by visit week using (n, mean, SD, geometric mean, CV, median, quartiles, minimum, and maximum). Concentrations less than LLOQ are imputed as LLOQ/2. A listing of all concentration data versus actual time and nominal time will be provided.

A longitudinal plot displays geometric mean of trough concentration versus week.

8 CONVENTIONS

8.1 Visit Definition

Visits are defined below. Subjects receive up to 24 weeks of study therapy and are followed for an additional 24 weeks. Windows are constructed for each visit in order to slot data. Labels for study periods and visits appear in listings and datasets.

Table 8.1-1: Visit Definition

Study Period Label	Visit Label	Visit Number	Target Day from Start of Study Period	Visit Window
PRE-TREAT	PRE-TREAT	1	1	< 1 day ^a
ON-TREAT	DAY 1	2	1	1 - 4 days
	WEEK 1	3	7	5 days - 11 days
	WEEK 2	4	14	12 days - 3 weeks
	WEEK 4	5	28	> 3 weeks - 6 weeks
	WEEK 8	6	56	> 6 - 10 weeks
	WEEK 12	7	84	> 10 - 14 weeks
	WEEK 16	8	112	> 14 - 18 weeks
	WEEK 20	9	140	> 18 - 22 weeks
	WEEK 24	10	168	> 22 weeks
FOLLOW-UP	F/U WEEK 4	11	21	> 1 - 8 weeks

[figure not shown]
Table 8.1-1: Visit Definition

Study Period Label	Visit Label	Visit Number	Target Day from Start of Study Period	Visit Window
	F/U WEEK 12	12	77	> 8 - 18 weeks
	F/U WEEK 24	13	161	> 18 weeks

^a See [Section 6.1](#), Study Periods, for classification of measurements on Day 1 (first dose of active study therapy) as pre-treatment or on-treatment depending on the data domain.

For the definitions of time measurement, windows around planned measurement times, and study day/week, refer to the Core SAP Section 8.1.

8.2 Domain Derivations

9 CONTENT OF REPORTS

9.1 Planned Analyses

- The analysis for the primary endpoint will be performed after all subjects have reached post-treatment Week 12 (SVR12) ;
- The final analysis (SVR24) will be performed at study completion.

9.2 Listings

Refer to Core SAP Section 9.2.

APPENDIX 1 RELEVANT PROTOCOL DEVIATIONS

The relevant protocol deviations that can be programmed from the database are identified below.

The list would be updated as appropriate if, in the course of monitoring the study, additional protocol deviations are found and considered relevant.

APPENDIX 2 STANDARD ERROR ESTIMATE OF THE MEDIAN

Refer to Core SAP Appendix 2.

DOCUMENT HISTORY

Version Number	Author(s)	Description
1.0	[REDACTED]	Initial version
